4.1.4 Selection and timing of doses for each patient

Prior to inclusion of a new patient in the phase I part the investigator has to confirm the actual dose tier of BI 6727 for the patient with the clinical monitor of the sponsor who oversees the dose escalation steps according to the safety data of patients from all trial sites.

BI 6727 will be administered as an intravenous infusion under the supervision of the investigator or designated personnel. Subcutaneous cytarabine injections will be administered according to the SPC.

The trial drugs may be administered at any time during the day. In case the second dose of BI 6727 is missed for administrative reasons the respective dose will be administered on the following two days. In case a dose of cytarabine is missed for administrative reasons the respective dose will not be administered at a later time (any missed cytarabine dose must be documented in the eCRF).

At the end of each treatment cycle, the response to treatment will be assessed. To continue treatment with further cycles, the following criteria must be met:

- 1.) Absence of disease progression (see [section 5.1.1](#))
- 2.) Neutrophils $\geq 500 / \mu\text{L}$ ($0.5 \times 10^9 / \text{L}$) and platelets $\geq 25,000 / \mu\text{L}$ ($25 \times 10^9 / \text{L}$); unless CTCAE grade 4 neutropenia or thrombopenia was preexistent
- 3.) Acceptable tolerability (in case of DLT, patients may continue therapy only after recovery from DLT to CTCAE levels which allow further therapy and only with a reduced dose), and recovery from drug-related cardiac toxicity.

In case criterion 2 is not fulfilled, the peripheral blood should be re-evaluated for up to three weeks. As soon as criterion 2 is met the treatment should be continued (unless other criteria for discontinuation or withdrawal apply, see [section 6.3](#)). A delay of haematopoietic reconstitution (i.e criterion 2 unmet) for more than three weeks after the end of the treatment cycle qualifies for DLT in patients with CRi or PR (see [section 5.2.3](#)). Any case of a delay in treatment cycle should be communicated to the clinical monitor of Boehringer Ingelheim. Progressive disease will lead to discontinuation of treatment.

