5.2.3 Dose limiting toxicity

Dose limiting toxicity (DLT) is defined as drug related CTCAE grade ≥ 3 non-haematological toxicity (excluding: untreated nausea, untreated vomiting, CTCAE grade 3

untreated diarrhoea, CTCAE grade 3 "febrile neutropenia" and CTCAE grade 3 "infection with grade 3 or 4 neutrophils").

In patients with CRI or PR, persistent CTCAE grade 4 neutropenia or thrombocytopenia until three weeks after the end of the treatment cycle will be regarded a DLT unless the respective grade 4 cytopenia was pre-existent. In patients who required platelet substitution to maintain a CTCAE grade < 4 before treatment, a CTCAE grade 4 thrombocytopenia after treatment does not constitute a DLT.

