5.2.4 Maximum tolerated dose

The MTD is defined as the highest dose at which six patients have been treated and less than two patients experienced DLT within the first cycle of treatment. The MTD will be defined based on safety data from the first cycle only. However, the data from later treatment cycles will be considered for future development of BI 6727 in this indication. To determine the MTD of BI 6727 on days 1 + 15 in combination with LD Ara-C (schedule A), the dose escalation starting with 150 mg BI 6727 will be conducted following the "3 + 3 design with de-escalation" as described in [section 4.1.3](#). To determine the MTD of BI 6727 on day 1 + 15 monotherapy (schedule B), the dose escalation starting with the BI 6727 MTD determined in schedule A will be conducted following the "3 + 3 design with de-escalation" as described in [section 4.1.3](#).

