5.2.7 ECG

12-lead resting ECG will be performed in all patients at the screening visit and at the EoT visit.

For patients in treatment schedules A and B ECGs will be recorded with every infusion of BI 6727 (before the start and immediately before the end of the BI 6727 infusion), additional ECGs will be recorded in cycle 1. In cycle 1 at visit 1 and 4, and at visit 1 in cycle 2 the ECGs must be performed at the related PK sampling time points. All ECGs have to be digitally recorded using dedicated equipment provided by a contract research organisation (CRO; [REDACTED]) at the following time points:

After approval of Protocol Revision I, ECGs should be recorded prior to and at the end of volasertib infusions. No digital and triplicate recording is required anymore. ECGs can be recorded with a local ECG machine.

- Visit 1 (day 1) of cycle 1
 - ! prior to start of infusion of BI 6727
 - ! immediately before the end of infusion of BI 6727 (1:00 hour). The infusion should not be finished yet at that sampling time point.
 - ! 2 hours after the start of infusion;
 - ! 4 -6 hours after the start of infusion
 - ! 24 hours after the start of the infusion
- Visit 4 (day 15) of cycle 1
 - ! prior to start of infusion of BI 6727

- ! immediately before the end of infusion of BI 6727 (1:00 hour). The infusion should not be finished yet at that sampling time point.
- ! 2 hours after the start of infusion;
- ! 4 -6 hours after the start of infusion

- Visit 1 (day 1) and visit 4 (day 15) of every cycle \geq 2:

- ! prior to start of infusion of BI 6727
- ! immediately before the end of infusion of BI 6727 (1:00 hour). The infusion should not be finished yet at that sampling time point.

The recording will be checked for pathological results (to be recorded as AEs) by the investigator. In addition, a centralized evaluation of all 12-lead ECGs recorded will be performed by a CRO (████████).

After approval of Protocol Revision I, transmissions for central ECG analysis will be discontinued.

In addition, ECGs should be done whenever the investigator deems necessary.

In case of drug related ECG changes, additional ECG monitoring will be performed in the respective and later cycles of treatment.

In case of QTcF > 470 ms prior to the planned start of infusion of BI 6727, the trial drug should not be administered.

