6.3 REMOVAL OF PATIENTS FROM THERAPY OR ASSESSMENT

A patient has to be withdrawn from the trial in case one of the following criteria applies:

- ! A patient withdraws consent (patients are free to discontinue their participation in this trial at any time without the need to justify this decision).
- ! A treatment cycle has been delayed for more than three weeks for other than medical reasons
- ! A patient is no longer able to participate in the trial (e.g. AEs unrelated to therapy or disease progression, surgery, concomitant diagnoses, concomitant therapies or administrative reasons). The investigator may also stop a patient's participation, if the patient is no longer able to attend trial visits.
- ! A patient is being administered forbidden concomitant medication (refer to [section 4.2.2](#))

A patient can be withdrawn after discussion between the sponsor and the investigator if eligibility criteria are violated and / or the patient fails to comply with the protocol.

All withdrawals will be documented and the reason for withdrawal recorded and discussed, as necessary, in the final report of the trial. As soon as a patient is withdrawn from the trial, the next scheduled visit and the EoT have to be performed if feasible. Every effort should be made to follow-up patients in case an AE is still ongoing at the time of withdrawal. Patients who withdraw after assignment / randomisation and prior to the first treatment will not be included in the analysis data set for efficacy evaluation. They will be entered into the trial database, the reason for withdrawal will be documented and reported descriptively as well as by patient listing in the final trial report.

A patient has to discontinue trial drug administration in case

- ! DLT occurs which does not recover to a degree that allows treatment continuation or a second episode of DLT occurs in this patient or
- ! PD develops, including deterioration of general condition due to disease progression

Patients included in the phase I part who have not completed at least one cycle will be replaced unless they discontinued the trial due to drug-related AEs.

Patients allocated to treatment schedules A or B in the phase I part of the trial who for administrative reasons omitted the second infusion in the first 4-week cycle and were unable to receive the missed infusion within the next two days will be replaced.

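### Phase I patients who stop in cycle 1 for drug-related toxicity short of a DLT are neither DLTs nor replaced, so they count as DLT-free when the MTD is set

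*Protocol*

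**What the plan says.** - **Replacement (Protocol 6.3).** Phase I patients who have not completed at least one cycle "will be replaced unless they discontinued the trial due to drug-related AEs". A separate rule replaces BI 6727 patients "who for administrative reasons omitted the second infusion in the first 4-week cycle" and could not receive it within the next two days. Neither rule mentions an infusion omitted for toxicity.
- **DLT (Protocol 5.2.3).** "Dose limiting toxicity (DLT) is defined as drug related CTCAE grade ≥ 3 non-haematological toxicity", with exclusions that include grade 3 febrile neutropenia and grade 3 infection with grade 3 or 4 neutrophils. Grade 4 neutropenia or thrombocytopenia counts only in patients with CRi or PR, only if it persists until three weeks after the cycle, and only if it was not there before.
- **MTD (Protocol 5.2.4).** The "highest dose at which six patients have been treated and less than two patients experienced DLT within the first cycle of treatment". No minimum exposure or observation is required of the six.
- **Withheld infusion (Protocol 5.2.7).** In case of "QTcF > 470 ms prior to the planned start of infusion of BI 6727, the trial drug should not be administered". The same section labels prolongation above 500 ms as grade 3.
- **Analysis sets.** Protocol 7.3 admits a phase I patient after one dose of BI 6727, and SAP 6.3 after one dose of either drug. Replaced patients stay in. SAP 5.1.1 defines the MTD from two or more DLTs in six, and SAP 5.2.6 takes DLTs from an eCRF question. Neither document defines a DLT-evaluable patient.

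**The concern.** The exception in 6.3 would be harmless if every drug-related stop were a DLT: the patient would count as an event and need no replacement. But the exception refers to drug-related AEs, and 5.2.3 sets a higher bar. Between the two lies a group whose toxicity ended treatment but is not an event. Under 5.2.4 each of them takes one of the six places and is scored as tolerating the tier, although they may have had only one of the two BI 6727 infusions.

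The MTD is the phase I primary endpoint. It is also the starting dose of schedule B (Protocol 4.1.3) and the basis for the phase IIa dose. The situation is foreseeable: Protocol 1.2.1 reports that reversible haematotoxicity was dose limiting in the earlier trial and that QTcF prolongation was dose dependent.

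**Working it through.** **Step 1: follow three patients through the text.**

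| Patient in cycle 1 | DLT (5.2.3)? | Replaced (6.3)? | Among the six (5.2.4)? |
|---|---|---|---|
| Stops on day 10 for drug-related grade 3 febrile neutropenia | No | No, the exception applies | Yes, DLT-free |
| Second infusion missed for administrative reasons, not given within two days | No | Yes | Place refilled |
| Second infusion withheld at QTcF 480 ms, stays on trial | Not by the grading in 5.2.7 | Unclear | Unclear |

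The third row depends on what completing a cycle means. If it requires both infusions, the general rule replaces this patient, who has not discontinued the trial. The separate administrative rule would then be largely redundant. That makes non-replacement the more natural reading, but it remains an inference.

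**Step 2: reproduce the protocol's figure.** Table 7.6: 1 gives the chance of at least two DLTs in six. With p = 0.42:

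1 − 0.58^6 − 6(0.42)(0.58^5) = 1 − 0.0381 − 0.1654 = 0.797, stated as 0.80.

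The entries for 0.40 and 0.45 also reproduce (0.767 and 0.836, stated as 0.77 and 0.84).

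**Step 3: let k of the six receive only the first infusion.** The documents give neither k nor the timing of risk, so both are assumptions. Splitting the risk of 0.42 equally over two infusions gives r = 1 − √0.58 = 0.238 per infusion. With 6 − k patients at risk 0.42 and k at risk r:

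- P(0) = 0.58^(6−k) × (1−r)^k
- P(1) = (6−k)(0.42)(0.58^(5−k))(1−r)^k + k·r·(1−r)^(k−1) × 0.58^(6−k)

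| k | P(0) | P(1) | P(at least 2) | P(at most 1) |
|---|---|---|---|---|
| 0 | 0.038 | 0.165 | 0.797 | 0.203 |
| 1 | 0.050 | 0.197 | 0.753 | 0.247 |
| 2 | 0.066 | 0.231 | 0.703 | 0.297 |
| 3 | 0.086 | 0.268 | 0.646 | 0.354 |

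If the k patients are instead treated as certain to be DLT-free, only 6 − k can contribute, and P(at least 2) is 0.697 for k = 1 and 0.559 for k = 2.

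**Step 4: keep two quantities apart.** The last column is the chance that six treated patients show at most one DLT. It is not the chance that escalation proceeds, because under Protocol 4.1.3 a result of 0 of 3 already suffices. That chance is (1−q)^3 + 3q(1−q)^5:

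- Full exposure, q = 0.42: 0.195 + 0.083 = 0.28.
- If 20% of patients (assumed) have risk 0.238, q = 0.8(0.42) + 0.2(0.238) = 0.384: 0.234 + 0.102 = 0.34.
- If that 20% have no DLT risk, q = 0.336: 0.293 + 0.130 = 0.42.

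**The case against.** **Existing safeguards.** Phase IIa opens only after a reviewed safety analysis and a favourable risk-benefit assessment (Protocol 3.1). The dose recommendation considers safety over all cycles (7.3.4) and may differ from the MTD (2.1). The sponsor's clinical monitor oversees each escalation step (4.1.4). AEs are reported for six weeks after the last dose (5.2.1), so a later DLT in a stopped patient can still be recorded. This stands, and it softens the effect on the phase IIa dose. It does not change the MTD count or the schedule B starting dose.

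**Frequency.** Nothing requires a patient to stop for grade 3 febrile neutropenia, and the documents do not say how often drug-related stops short of a DLT occur. This also stands, so the figures above show sensitivity and are not forecasts. The equal split of risk is a simplification too: in schedule A, cytarabine on days 1–10 may have been given in full.

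**Replacement can hide toxicity.** Keeping drug-related stops in the cohort preserves information. That is a fair point against replacement alone, and the reason the fix includes a repeat count.

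**Stronger readings a reader might infer.** One is that anyone who misses the second infusion goes unreplaced; 6.3 does replace administrative misses that are not made up. Another is that the patient with withheld QTcF dosing certainly counts as DLT-free; the text leaves this open. A third is that the MTD ends up too high overall. Protocol 7.6.1 says the design tends to give a low estimate, and only a shift relative to the same rule under full exposure is shown.

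**Conclusion.** The gap is real for patients who stop in cycle 1 for drug-related toxicity short of a DLT. It follows directly from Protocol 5.2.3, 5.2.4 and 6.3 read together, and nothing in the SAP closes it. For infusions withheld for toxicity without a stop, the fault is an ambiguity that must be resolved.

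The direction is upward relative to the same 3+3 rule with fully exposed patients. The size cannot be estimated from the documents. At a true risk of 0.42 split equally over the infusions, the stated 0.80 chance of seeing two or more DLTs falls to 0.75, 0.70 or 0.65 with one, two or three affected patients. Its complement rises from 0.20 to between 0.25 and 0.35. It would be wrong to report that complement as the tier's 3+3 pass probability, which is 0.28 at full exposure.

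**What to change.** 1. In Protocol 5.2.4 and 6.3, read together with 5.2.3, and in SAP 5.1.1 and 6.3, state who counts among the six. An MTD-evaluable patient either had a cycle 1 DLT, or received both BI 6727 infusions and was observed for the whole of cycle 1. Replace all others for the MTD count, and say what completing a cycle means.
2. In the phase I safety analysis (Protocol 7.3.4), show per dose tier the numbers treated, given both infusions, with a DLT, and with a drug-related stop or omitted infusion that was not a DLT.
3. Repeat the MTD count with this last group as events, so that replacement does not remove toxicity from view.

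No dose and no DLT criterion changes. The cost is protocol and SAP wording, one table, one repeat count and possibly a few more replacement patients. If phase I is already complete, replacement can no longer be applied. The table and the repeat count still can, since SAP section 3 covers both the safety update after phase I and the final report.

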7. STATISTICAL METHODS AND DETERMINATION OF SAMPLE SIZE

The trial will be performed in two parts, a phase I part and a phase IIa part. In the phase I part of the trial, BI 6727 will be investigated as monotherapy and in combination with LD-Ara-C in patients with relapsed/refractory AML. In the phase I part, the dose of BI 6727 will be escalated to determine the maximum tolerated dose (MTD) of BI 6727 monotherapy and BI 6727 in combination with LD-Ara-C in relapsed/refractory AML patients who are ineligible for other treatment options.

In the phase IIa part, the combination of BI 6727 at MTD with LD-Ara-C and LD-Ara-C monotherapy will be investigated to determine the efficacy of the combination schedule in comparison to LD-Ara-C monotherapy in previously untreated AML patients that are considered ineligible for intensive treatment.

7.1 STATISTICAL DESIGN - MODEL

The trial will be performed as an open label study. In phase I patients will not be randomized; they will be assigned to the treatment schedule that is being filled at the time the patient is ready to enter the trial (BI 6727 monotherapy and BI 6727 in combination with LD-Ara-C, respectively). In phase IIa patients will be randomly allocated to one of the two different treatment schedules BI 6727 in combination with LD-Ara-C and to a monotherapy schedule with LD-Ara-C only, respectively.

To determine the MTDs in the phase I part, cohorts of patients will be entered sequentially into escalating dose tiers using the 3+3 design with dose de-escalation (R04-0569) (see section 4.1.3). Intra-individual dose escalation will be allowed according to the rules specified in section 4.1.4.

7.2 NULL AND ALTERNATIVE HYPOTHESES

The analyses will thoroughly explore all aspects of the efficacy and safety of BI 6727 in combination with LD-Ara-C. All analyses in this study are descriptive and exploratory by nature. Any statistical tests are performed only to provide a statistical framework from which to view the results and providing aid for planning further studies. No formal statistical tests are foreseen.

7.3 PLANNED ANALYSES

Two analysis populations are defined for efficacy and safety analyses. For the phase I part the full analysis set (phase I) is defined, in analogy to the intention to treat population as the treated set with respect to phase I; i.e. all patients of phase I who have received at least one single dose of BI 6727 will be considered, including the patients who have been replaced for any reason (see section 6.3).

For the phase II part the full analysis set (phase II) is defined, in analogy to the intention to treat population as the treated set with respect to phase II; i.e. all patients of phase II who have received at least one single dose of either BI 6727 or cytarabine will be considered.

No per protocol population will be used for analyses. However protocol violations will be described.

7.3.1 Primary analyses

7.3.1.1 Assessment of the MTD and derived variables for first cycle only

One primary objective for this study is the tolerability and safety of BI 6727 as monotherapy and in combination with cytarabine, respectively, as reflected by the MTD (for definition of MTD please refer to [5.2.4](#)).

In addition, to determine the MTD, an analysis on conditional probabilities for a DLT given the dose will be done, based on the logistic regression model.

For the analysis of the tolerability and safety, please refer to [section 7.3.3](#).

7.3.1.2 Assessment of the primary efficacy endpoint and derived variables

The primary endpoint for efficacy is best objective response derived from the data of all cycles. The primary analysis will be done for all patients of the full analysis set (phase II) for all treatment schedules separately. Each patient will be assigned to one of the response categories described in [section 5.1.1.1](#).

Each patient's best response will be used as a primary measure. To describe response over time, the proportions of patients in each response category will be tabulated at specified time intervals.

The number of patients with objective response (best response is CR or CRi) will be summarised. Patients will be followed up for assessment of response and progression until they progress, receive any other anti-leukaemia therapy, die, or until the trial ends. The observed length of follow-up and the number of patients available for analysis at each time point will determine the period of time covered in tables and figures.

7.3.1.3 Statistical group comparison

All statistical group comparisons will be performed with respect to the full analysis set (phase II)

The comparison of the treatment schedule to the control schedule will be based on the conditional power approach and on a stopping for futility check. The conditional power for showing superiority of a treatment schedule with respect to the control schedule at a later time point will be evaluated. The conditional power will be compared to a given fixed value that is based on assumptions for the information time and for the significance level of the (hypothetical) statistical test at a later time point (see also [section 7.6.2](#)).

Odds ratios, confidence intervals, and Fisher's exact test will be used to compare treatments in an exploratory manner if appropriate. Additionally, the conditional power for showing superiority at a later time point will be evaluated. The exploratory nature of these analyses will be considered when interpreting the significance levels. P-values derived from statistical tests smaller than 5% will only be reported as nominally significant regarding the small sample size in each treatment schedule.

7.3.2 Secondary analyses

7.3.2.1 Assessment of the secondary endpoints and derived variables

Secondary endpoints related to efficacy will be event free survival, overall survival, relapse-free survival, and remission duration.

Event free survival, overall survival, relapse-free survival

Event free survival (EFS) is defined as the duration of time from randomisation to time of treatment failure (i.e. PD), relapse from CR, or death from any cause, whichever comes first. Overall survival is the time from randomisation until death. Relapse-free survival is defined only for patients who achieve CR and is measured from the date of attaining CR until the date of recurrence or death from any cause, whichever occurs first.

In case there is no occurrence of death or treatment failures until the last visit of the trial the time will be censored. The percentage of patients who are event free will be displayed at monthly or greater time intervals as appropriate.

The causes of death will be summarised, along with whether death was plausibly related to disease progression.

Remission duration, response rate at different time points

Exploratory analyses will be performed to determine the remission duration and the response rate after specified time intervals. Analysis of remission duration will only be done for patients who achieve CR.

